5. STUDY POPULATION

5.1 SCREENING DATA

Patients with suspected sepsis will be identified at ED triage. After initial NEWS2 and assessment according to the current standard of care the eligibility criteria will be assessed and if no exclusion criteria apply, patients will be enrolled into the trial and randomised. A screening log of all eligible and randomised patients will be kept at each site so that any biases from differential recruitment will be detected. Tables will present the following summaries (overall and by study site): the number of days recruiting, number of patients screened, number of patients recruited, number of patients recruited per day, number of screened patients not recruited, and the reason for non-recruitment.

5.2 ELIGIBILITY

Participants are eligible for the trial if they meet all the following inclusion criteria and none of the exclusion criteria apply.

Inclusion criteria

• Patients ≥16 years presenting to the ED with suspected sepsis.

Exclusion criteria

- Currently on IV antibiotics.
- Current use of any chemotherapy agent associated with myeloablation/suppression.
- History of solid organ transplantation, allogeneic bone marrow, or stem cell transplantation within 3 months prior to consent.
- Patients requiring urgent surgical intervention.
- Presence of an advance directive to withhold life-sustaining treatment (patients not wishing to receive cardiopulmonary resuscitation (CPR) may qualify provided they receive all other resuscitative measures e.g., respiratory support, fluid resuscitation).

5.3 RECRUITMENT

As a deferred consent model is being used, patients and their relatives will be informed that a study is ongoing, but a lengthy consent discussion will not be had so as not to delay treatment. Should the patient or consultee wish not to take part at this point, then the decision should be respected, and the patient should not be enrolled into the trial. Patients who have given verbal consent will be

TPL/008/2(v1.0)

Canolfan Ymchwil Treialon

Short title:	ISAP / SAP Template

randomised regardless of baseline NEWS2. The process is described in the participant flow diagram (PRONTO Protocol Version 3.1 dated 23/10/23; Section 3; Figure 1).

5.4 TIERED CONSENT PROCESS

Due to time constraints in managing suspected sepsis, patients will be randomised into either the standard care arm or interventional arm on diagnosis with suspected sepsis prior to consent being obtained. The participant will be approached within 72 hours of randomisation to complete the formal informed consent process. The process is described in the participant consent flowchart (PRONTO Protocol Version 3.1 dated 23/10/23; Section 9.3; Figure 2). During this process participants can consent to different aspects of the trial using a tiered consent approach.

Participants can agree to the following aspects of the study:

- 1. Information collected as part of the trial and data from medical records from the date of randomisation up to the date of consent can be used in the trial.
- 2. Data from medical records can be collected from the date of randomisation to 90 days after this date.
- 3. Participant to be contacted by research staff at day 28 and day 90 to ask about health, wellbeing and any further medical treatment they may have received.

5.5 WITHDRAWAL/FOLLOW UP

If a patient does not wish to take part in any aspects of the trial, they will be withdrawn from the study and all clinical data up until that point will be removed from the study database. Participants have the right to withdraw consent for the use of clinical data collected in any aspect of the trial at any time. A participant's care will not be affected at any time by declining to participate or withdrawing from the trial.

5.5.1 LEVEL OF WITHDRAWAL

Some participants may wish to withdraw the use of the data upon first approach for deferred consent, following the intervention. If a participant provides deferred consent at this stage but subsequently withdraws from the trial, clear distinction must be made as to what aspect of the trial the participant is withdrawing from. These aspects could be:

- 1. Partial withdrawal from further data collection (questionnaires, clinical assessments)
- 2. Complete withdrawal from further data collection
- 3. Withdrawal of permission to use data already collected.

5.5.2 TIMING OF WITHDRAWAL

The numbers (with reasons) of losses to follow-up (dropouts and withdrawals) over the course of the trial (baseline, randomisation, treatment phase, day 28 and day 90 follow-up) will be presented in a CONSORT flow diagram.

TPL/008/2(v1.0)

Canolfan Ymchwil Treialon

Short title:	ISAP / SAP Template	
--------------	---------------------	--

5.5.3 REASONS FOR WITHDRAWAL

Participants who consent and subsequently withdraw are invited to complete a withdrawal form. If they decline, the withdrawal form should be completed by the researcher/clinician based on information provided by the participant. Participants will be identified as lost to follow-up if it is not possible to contact them directly for 4 weeks post day 90.

5.5.4 PRESENTATION OF WITHDRAWAL/LOSS TO FOLLOW-UP

We will report frequencies and percentages of participant withdrawal, overall and by trial arm, broken down by level, timing, and (where available) reason for withdrawal.

5.6 BASELINE PARTICPANT CHARACTERISTICS

- 5.6.1 LIST OF BASELINE DATA
 - Age
 - Gender
 - Ethnicity
 - Timing of initial assessments and ED admission
 - Duration of symptoms
 - Initial diagnosis
 - Initial treatment
 - History of oral antibiotic use in 14 days prior to admission
 - Comorbidities (Charlson Comorbidity Index)
 - COVID-19 status
 - C-reactive protein (CRP) at baseline

5.6.2 DESCRIPTIVE STATISTICS

Participant characteristics will be summarised as frequencies and percentages, means and standard deviations, or medians and interquartile ranges, depending on the type of variable, for all randomised participants, overall and by trial arm, as well as for analysis populations as defined in Section 4.3, and by risk category based on NEWS2 score at baseline (≤ 4 , 5-6 and ≥ 7).

6. ANALYSIS

- 6.1 OUTCOME DEFINITIONS
- 6.1.1 PRIMARY OUTCOME(S)

The study will use the following as co-primary outcomes:

- IV antimicrobial initiation at 3 hours (binary outcome)
- 28-day mortality (binary outcome)

TPL/008/2(v1.0)

Canolfan Ymchwil Treialon

Short title: ISAP / SAP Template

Decisions about effectiveness using these co-primary outcomes will be made based on Table 3.

Table 3: determining whether the intervention is effective using the co-primary outcomes.

	Reduced antibiotic initiation	Same or more antibiotic initiation
Decreased mortality	Effective	Effective
Equivalent mortality	Effective	Not effective
Increased mortality	Not effective / harmful	Not effective / harmful

6.1.2 TIMING, UNITS AND DERIVATION OF PRIMARY

We will assess 28-day mortality from the date of randomisation, and IV antimicrobial initiation within 3 hours of ED admission. Both outcomes are recorded in binary format.

6.1.3 LIST OF SECONDARY OUTCOMES

- 1. Time until initiation of IV antibiotic therapy
- 2. Late IV antibiotic initiation antibiotics commenced after 3 hours
- 3. Number of days on IV antibiotics (during admission and total over the first 28 days)
- 4. Number of days on any antibiotics (during admission and total over the first 28 days)
- 5. Number of days on broad spectrum antibiotics (IV and oral), defined by number of days on an 'Watch/Reserve' group antibiotic as defined by WHO AWaRe Classification Database (during admission and total over the first 28 days)
- 6. Critical care admission (ICU or HDU) at any point during hospital admission
- 7. Length of ICU/HDU stay (overnight stays)
- 8. Length of hospital stay (overnight stays)
- 9. Adverse antibiotic outcomes (including *C. difficile* cases and hospital acquired infections (HAIs))
- 10. Readmission to hospital within 90 days (defined as readmission due to original diagnosis as per CRF)
- 11. Mortality within 90 days (and time until death)
- 12. Health utility (EQ-5D-5L) at 28 and 90 days
- 13. Health resource usage (described in the health economics analysis plan)
- 14. Feasibility of implementing PCT testing alongside NEWS2 scoring in EDs (described in the qualitative analysis plan)
- 15. Acceptability of implementing PCT testing alongside NEWS2 scoring in EDs, to patients, carers, and clinicians (described in the qualitative analysis plan)

6.1.4 ORDER OF TESTING

TPL/008/2(v1.0)

Canolfan Ymchwil Treialon

Short title: ISAP / SAP Template

Not applicable.

6.1.5 TIMING, UNITS AND DERIVATION OF SECONDARIES

Individual timing and measurements of secondary outcomes are described in the table below:

Outcome	Measure	Time frame
Antibiotic initiation	Time until initiation Late IV antibiotic initiation (after 3 hours) (yes/no)	In ED/hospital
Antibiotic usage	No of days on IV antibiotics* No of days on all antibiotics* No of days on broad spectrum antibiotics (Watch/Reserve)*	In hospital and total over first 28 days
Critical care usage (ICU and HDU)	Admitted to ICU or HDU (yes/no) No of overnight stays in ICU and HDU	In hospital
Hospital stay	No of overnight stays in hospital	In hospital
Antibiotic adverse outcomes	Anticipated drug reactions include diarrhoea, C. difficile , acute kidney injury, hearing loss, etc.	In hospital
Readmission to hospital	People with one or more readmissions	After discharge within 90 days
Mortality	Mortality within 90 days No of days until death*	90 days
Health utility	EQ-5D-5L	28 and 90 days

*Days will be counted if an event occurs at any time between 00:00 and 23:59.

6.2 ANALYSIS METHODS

- 6.2.1 LIST OF METHODS AND PRESENTATION
- **6.2.1.1 BASELINE DEMOGRAPHICS ANALYSIS**

Baseline data (e.g., age, gender, comorbidities, etc.) will be summarised by trial arm using appropriate descriptive statistics (section 5.5.2) and for those who completed follow-up compared to those lost to follow-up.

6.2.1.2 PRIMARY OUTCOME ANALYSIS

We will use complete case analysis for the co-primary outcomes, meaning that we will only include participants with valid responses to both co-primary outcomes in the primary analysis. We will fit separate two-level logistic regression models (patients nested within sites) to model both co-primary outcomes, controlling for baseline NEWS2 score (minimisation variable). Results will be reported as risk differences with corresponding confidence intervals (calculated via the delta method (Norton et al., 2013)); a two-sided 90% interval for 28-day mortality (OBF adjusted to 90.18%), and a two-sided

TPL/008/2(v1.0)

Canolfan Ymchwil Treialon

Short title: ISAP / SAP Template	
----------------------------------	--

95% interval for IV antibiotic initiation at 3 hours (OBF adjusted to 95.04%). Non-inferiority in 28-day mortality will be concluded if the upper bound of the confidence interval is below +2.5% on the risk difference scale.

The individual analyses for the co-primary outcomes and corresponding inferences are described in the table below:

128-day mortality228-day mortality	Non-inferiority test with a margin of 2.5% H ₀ : $p_2 - p_1 \ge 0.025$ Superiority test	O'Brien-Fleming alpha spending (one-sided alpha = 0.05) Reject null if P < 0.0491 Critical value = 1.654 O'Brien-Fleming alpha spending (one-sided alpha = 0.05)
= = = = = = = = = = = = = = = = = = = =	Superiority test	O'Brien-Eleming alpha spending (one-sided alpha = 0.05)
	$H_0: p_1 - p_2 \le 0$	Reject null if P < 0.0491 Critical value = 1.654
3 IV antibiotic initiation at 3 hour	H ₀ : $p_1 - p_2 \neq 0$	O'Brien-Fleming alpha spending (two-sided alpha = 0.05) Reject null if P < 0.0496 Critical value = 1.964 the control and intervention arm, respectively.

 Table 5: Inferences for analyses of co-primary outcomes

It has been recognised that the option to stop the trial early in sequential designs introduces bias to the standard maximum likelihood estimator (MLE) (Cox, 1952). Therefore, we will also calculate unconditional bias-adjusted point estimates. We will derive the bias-adjusted maximum likelihood estimates proposed by Whitehead, by subtracting an estimate of the bias from the MLE (Whitehead, 1986). We will also calculate the uniformly minimum variance unbiased estimator (UMVUE) using the Rao-Blackwell technique. We will calculate the unconditional bias-adjusted point estimates, as we want to determine the point estimates regardless of the stage at which the trial stops. We are interested in the bias as averaged over all possible stopping times, weighted by the respective stage-wise stopping probabilities (Robertson et al., 2023, Grayling & Wason, 2022).

Table 6: Summary of analyses of primary outcomes

Outcome	Analysis	Covariates
	Primary analysis:	Trial arm and baseline NEWS2

Canolfan Ymchwil Treialon

IV antimicrobial	Two-level logistic regression	Trial arm, baseline NEWS2, age,
initiation at 3 hours		number of comorbidities and gender
(superiority)	Secondary analysis:	Trial arm and baseline NEWS2
	Two-level logistic regression with	Trial arm, baseline NEWS2, age,
	bias-adjusted point estimates	number of comorbidities and gender
	Subgroup analyses:	Trial arm, baseline NEWS2, and the
	Two-level logistic regression	organ system of the infection (lower
	(interaction test by model	urinary tract, lower respiratory, intra-
	comparison)	abdominal, bacteraemia, skin, soft
		tissues, etc.)
		Trial arm, baseline NEWS2, and risk
		category based on NEWS2 score at
		baseline (≤4, 5-6 and ≥7)
		Trial arm, baseline NEWS2, and
		managed as suspected COVID-19
		during admission (yes/no)
		Trial arm, baseline NEWS2, and has a
		positive COVID-19 test result +/- 5 days
		from admission (yes/no)
		Trial arm, baseline NEWS2, and PCT
		machine used at the time of
		recruitment (BRAHMS PCT-
		direct/PathFast BRAHMS PCT)
		Trial arm, baseline NEWS2, and
		recruitment date (before 01/12/21,
		between 01/12/21 and 30/11/22, after
		30/11/22)
		Trial arm, baseline NEWS2, and level of
		site ED crowding (upper, middle and
		lower tercile of national monthly
		figures)
	Complier average causal effect	Trial arm, baseline NEWS2, and
	(CACE)	intervention adherence
28-day mortality	Primary analysis:	Trial arm and baseline NEWS2
(non-inferiority)	Two-level logistic regression	Trial arm, baseline NEWS2, age,
	number of comorbidities	
	Secondary analysis:	Trial arm and baseline NEWS2
	Two-level logistic regression with	Trial arm, baseline NEWS2, age,
	bias-adjusted point estimates	number of comorbidities and gender
	Subgroup analyses:	Trial arm, baseline NEWS2, and the
		organ system of the infection (lower
		urinary tract, lower respiratory, intra-
		unitary tract, lower respiratory, intra-

Short title: ISAP / SAP Template

Canolfan Ymchwil Treialon

Short title:	ISAP / SAP Template

Two-level logistic regression	abdominal, bacteraemia, skin, soft
(interaction test by model	tissues, etc.)
comparison)	Trial arm, baseline NEWS2, and risk
	category based on NEWS2 score at
	baseline (≤4, 5-6 and ≥7)
	Trial arm, baseline NEWS2, and
	managed as suspected COVID-19
	during admission (yes/no)
	Trial arm, baseline NEWS2, and has a
	positive COVID-19 test result +/- 5 days
	from admission (yes/no)
	Trial arm, baseline NEWS2, and PCT
	machine used at the time of
	recruitment (BRAHMS PCT-
	direct/PathFast BRAHMS PCT)
	Trial arm, baseline NEWS2, and
	recruitment date (before 01/12/21,
	between 01/12/21 and 30/11/22, after
	30/11/22)
	Trial arm, baseline NEWS2, and level of
	site ED crowding (upper, middle and
	lower tercile of national monthly
	figures)
Complier average causal effect	Trial arm, baseline NEWS2, and
(CACE)	intervention adherence

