4.1.1 ADJUSTMENT FOR MULTIPLICITY

TPL/008/2(v1.0)

Canolfan Ymchwil Treialon

Short title:	ISAP / SAP Template

We have used the O'Brien-Fleming type alpha spending method to adjust the interim analysis and final analysis level of significance. Adjustment for multiplicity of endpoints is not required because they are co-primary, therefore the resulting test procedure is an intersection-union test (Offen et al., 2007).

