4.3 ANALYSIS POPULATION

The primary analysis population will include all participants with a completed 'record of consent' form (completed by participants with capacity, a personal consultee if a participant lacks capacity, or a nominated consultee if a personal consultee cannot be identified, or if the participant died prior to obtaining consent) regardless of protocol deviations and adherence, and according to their randomised allocations (intention to treat), with complete data for both co-primary outcomes. A

TPL/008/2(v1.0)

[figure not shown]
Canolfan Ymchwil Treialon

Short title:	ISAP / SAP Template

participant is considered to have complete 28-day mortality data if they have either been confirmed to have died within 28 days or they are known to have been alive at day 28. A sensitivity analysis will be performed including all participants for whom consent has been obtained with complete data for at least one of the co-primary outcomes.

A secondary/sensitivity analysis will estimate the complier average causal effect (CACE) to account for departures from the randomised intervention. For the purposes of this sensitivity analysis, we will define different analysis populations depending on the level of adherence with the PCT-guided algorithm (Figure 3):

- Patients randomised to PCT-guided care in whom a PCT test is done, and a PCT result is available
- Patients randomised to PCT-guided care in whom a PCT test is done, a PCT result is available, and the clinician has seen the PCT result
- Patients randomised to PCT-guided care in whom a PCT test is done, a PCT result is available, the clinician has seen the PCT result and followed the algorithm exactly.

Canolfan Ymchwil Treialon

Short title:	ISAP / SAP Template

Figure 3: Flow diagram defining the different analysis populations in participants randomised to PCT-guided care

We will include a 4 by 4 table comparing the outcomes of the clinical risk assessment and the risk stratification/algorithm (Appendix Table A1).

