6.2.1.3 SECONDARY OUTCOME ANALYSIS

All secondary analyses will be performed on an intention to treat basis using the primary analysis population as defined in section 4.3, utilising two-level models to allow for patients nested within sites.

Table 7 – Summary of secondary analyses

	Outcome	Analysis	Covariates
1	Time until initiation of IV antibiotic therapy	We will present the result as a groupwise boxplot with median and range of number of hours. Cox regression analysis will be used, with the results reported as hazard ratios (HR) and 95% confidence intervals. We will also produce a Kaplan Meier plot and cumulative incidence plot.	 a) Trial arm and baseline NEWS2 b) Trial arm, baseline NEWS2, age, number of comorbidities and gender

TPL/008/2(v1.0)

Canolfan Ymchwil Treialon

Short title: ISAP / SAP Template

2	Late IV antibiotic initiation – antibiotics commenced after 3 hours	We will report the groupwise frequency and percentage of late initiations. Logistic regression will be used, with the results reported as odds ratios (OR) and 95% confidence intervals.	a) b)	Trial arm and baseline NEWS2 Trial arm, baseline NEWS2, age, number of comorbidities and gender
3	Number of days on IV antibiotics (during admission) Number of days on IV antibiotics (total over the first 28 days)	We will present the result as a groupwise boxplot with median and range of number of days. Poisson regression analysis will be used, with results reported as incidence rate ratios (IRR) and 95% confidence intervals.	a) b)	Trial arm and baseline NEWS2 Trial arm, baseline NEWS2, age, number of comorbidities and gender
4	Number of days on any antibiotic (during admission) Number of days on any antibiotic (total over the first 28 days)	We will present the results as a groupwise boxplot with median and range of number of days. Poisson regression analysis will be used, with results reported as IRRs and 95% confidence intervals.	a) b)	Trial arm and baseline NEWS2 Trial arm, baseline NEWS2, age, number of comorbidities and gender

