6.2.5 SENSITIVITY ANALYSES

The primary analysis described in section 6.2.1 uses the joint complete case population for both coprimary outcomes. As a sensitivity analysis we will repeat the analysis using the complete case populations of each of the co-primary outcomes individually (i.e., including participants with valid responses to at least one of the co-primary outcomes) using the same methods as described in section 6.2.1.

A sensitivity analysis will estimate the CACE to account for departures from the randomised intervention. For the purposes of this sensitivity analysis, we will define different analysis populations depending on the level of adherence to the PCT-guided algorithm (Figure 3): TPL/008/2(v1.0) CONFIDENTIAL Page 26 of 38

Canolfan Ymchwil Treialon

Short title:	ISAP / SAP Template

- Patients randomised to PCT-guided care in whom a PCT test is done, and a PCT result is available
- Patients randomised to PCT-guided care in whom a PCT test is done, a PCT result is available, and the clinician has seen the PCT result
- Patients randomised to PCT-guided care in whom a PCT test is done, a PCT result is available, the clinician has seen the PCT result and followed the algorithm exactly.

The non-inferiority margin is defined using a fixed risk difference of 2.5%. If the observed 28-day mortality in the control arm deviates from the 15% (by more than 3% points above or below) assumed in the sample size calculation, we will additionally repeat the primary analysis with the non-inferiority margin modified according to the power-stabilising arcsine transformation proposed by Quartagno et al. (2020 & 2023).

Also, the protocol allows patients to be recruited more than once into the study. If the proportion of repeatedly randomised patients exceeds 5%, we will perform a sensitivity analysis excluding repeat episodes.

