6.4 ADDITIONAL ANALYSES

We will compare the initial working diagnosis versus the final diagnosis by arm.

We may perform a linear regression analysis on an intention to treat basis using the primary analysis population as defined in section 4.3, utilising two-level models to allow for patients nested within sites, to explore the differences in Daily Defined Doses of antibiotics by arm.

The health economics and qualitative analysis plans are detailed separately from the SAP.

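### One joint complete-case set is used for both co-primaries and passed on to every secondary outcome, where nothing recovers the data it drops

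*SAP*

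**What the plan says.** SAP section 4.3 defines the primary population as consented participants "according to their randomised allocations (intention to treat), with complete data for both co-primary outcomes". Section 6.2.1.2 repeats the rule: "we will only include participants with valid responses to both co-primary outcomes in the primary analysis". The same section states that "We will fit separate two-level logistic regression models (patients nested within sites) to model both co-primary outcomes", and section 4.1.1 describes how the two results combine: "Adjustment for multiplicity of endpoints is not required because they are co-primary, therefore the resulting test procedure is an intersection-union test". No reason for a common set is given.

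Section 6.2.1.3 carries the set forward: "All secondary analyses will be performed on an intention to treat basis using the primary analysis population as defined in section 4.3". Section 6.4 does the same for the optional analysis of defined daily doses: "We may perform a linear regression analysis on an intention to treat basis using the primary analysis population as defined in section 4.3".

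Two provisions soften the rule.

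- Sections 4.3 and 6.2.5 plan a repeat of the co-primary analyses on each outcome's own complete cases, "including participants with valid responses to at least one of the co-primary outcomes".
- Section 6.3 adds multiple imputation as a sensitivity analysis if more than 5% of primary outcome data are missing.

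Both are written for the co-primary outcomes. Neither is stated to extend to the secondaries.

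**The concern.** An intersection-union test rejects overall only when each component null is rejected at its own level. That logic places no condition on who contributes to each component. With separate models, a participant whose 3-hour IV status is missing adds nothing to the antibiotic model but is fully informative for mortality, and the reverse also holds. Requiring both outcomes makes inclusion in one analysis depend on whether an unrelated variable was recorded after randomisation.

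For the secondary outcomes the consequence is concrete. Someone with unknown day-28 status leaves the analyses of time to IV antibiotics and late initiation, although both may be fully recorded. Someone with missing 3-hour IV status leaves the analyses of 90-day mortality, length of stay, readmission and EQ-5D-5L.

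The Cox model for time to death (Table 7, outcome 11) shows the selection most clearly. A participant censored before day 28 has no known day-28 status and is removed altogether. A participant who dies before day 28 is kept if IV status is known. Inclusion then depends on what is learned later, and the model loses the partial follow-up that it is built to use.

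**Working it through.** **The plan's own figures (section 3.3).**

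- Mortality, 15% in both arms, margin 0.025, one-sided 5%, 90% power: n per arm = (1.645 + 1.282)² × 2 × 0.15 × 0.85 / 0.025² = 3495 after rounding up, so 6990 in total. The SAP states 7002, a difference of 0.2%.
- Dropout: 7002 / 0.95 = 7371. The SAP states 7372.
- Antibiotic initiation, 90% against 80%, two-sided 5%, 90% power: 532 in total, as stated.

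The figures reproduce. What follows uses the group-sequential maximum of 7676 (section 3.3) and the final one-sided level of 0.0491 (section 3.5.2).

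**Joint loss and mortality power.** The SAP gives no missingness rates. Assume that each outcome is missing in a fraction m, independently of the other. The joint loss is then 1 − (1 − m)². Power = Φ(0.025/SE − 1.654), with SE = √(2 × 0.15 × 0.85 / (N/2)). This is a fixed-sample approximation at the final level.

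| m per outcome | Joint loss | N, mortality observed | Power | N, both observed | Power | Difference |
|---|---|---|---|---|---|---|
| 3% | 5.9% | 7446 | 91.4% | 7222 | 90.7% | 0.7 points |
| 4% | 7.8% | 7369 | 91.2% | 7074 | 90.2% | 1.0 point |

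The joint rule takes 7446 − 7222 = 224 or 7369 − 7074 = 295 participants with known vital status out of the mortality model.

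**A wider range.** Let 5% of mortality data be missing, leaving 7292 participants and 90.9% power. Requiring IV status as well gives:

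| IV status missing | N, both observed | Power |
|---|---|---|
| 1% | 7219 | 90.7% |
| 2% | 7146 | 90.4% |
| 5% | 6928 | 89.6% |
| 10% | 6563 | 88.1% |

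The cost is 73 to 729 participants and about 0.2 to 2.8 points of power.

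**Nested missingness.** Suppose instead that IV status is missing only where day-28 status is missing too. The joint set then equals the mortality-observed set, and the mortality test loses nobody. The antibiotic test loses everyone without day-28 status. With 5% missing it would use 7292 instead of 7676, against a requirement of 532.

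**Possible selection.** As an illustration, let IV status be missing for a fraction f of one arm only, with mortality of 30% in those participants instead of 15%. The observed risk in that arm becomes (0.15 − 0.30f)/(1 − f). This is lower by 0.3 points at f = 2% and by 0.8 points at f = 5%, against a margin of 2.5 points.

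**The secondaries.** No calculation is possible without missingness rates. The comparison of text is enough: section 6.2.1.3 imports the section 4.3 set for all secondary analyses, and section 6.2.5 relaxes it only for the co-primaries.

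**The case against.** **The co-primaries are already covered.** Section 6.2.5 plans the available-case analysis of each co-primary with the same methods. This stands. A reader might infer that valid mortality data are thrown away. They are not: they appear in a pre-specified analysis, and only the order of primary and sensitivity analysis is at issue.

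**Missingness may be largely nested.** Section 5.4 seeks consent within 72 hours of randomisation and lets a participant agree only to use of data up to consent. IV status at 3 hours would normally fall inside that window, while day-28 status generally needs the further tier. This makes IV status known with day-28 status missing the likelier pattern, and the loss then falls on the well-powered antibiotic test. This stands as a reading of the consent design, though the SAP gives no counts. It does not help the early secondary outcomes, which are the ones dropped under this pattern.

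**The bias is hypothetical.** A reader might infer that the non-inferiority test is biased. The shift of 0.3 to 0.8 points needs one-sided missingness and doubled mortality, and the SAP supports neither. Section 3.7 describes one collection process for all recruited participants. The figures show only what could happen.

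**The lost secondary data may be few.** Participants without day-28 status will often also lack 90-day mortality and 28-day antibiotic totals. This partly stands. The loss is probably greatest for early and in-hospital outcomes and for censored survival times, and its size is unknown.

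**The intention-to-treat label.** Section 4.3 states the complete-data condition openly, and any available-case set also depends on consent and an observed outcome. The label is loose but does not mislead. A common set may also suit the joint decision in Table 3, but that is a matter of presentation.

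**Conclusion.** The point holds, mainly for the secondary outcomes. There, participants with the outcome observed are excluded because a different variable is missing, and no stated analysis brings them back. The time-to-death model also loses anyone censored before day 28. For the co-primaries the restriction is unnecessary, but the planned sensitivity analysis contains the harm.

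The cost in mortality power is small: about 0.7 to 1.0 point under assumed independent missingness of 3% to 4% per outcome, with power still above 90%. A reader might infer from a joint loss of 5.9% to 7.8%, above the 5% dropout allowance, that the trial becomes underpowered. That does not follow, because the maximum of 7676 leaves enough participants at those rates. Power falls below 90% only at higher assumed rates, such as 5% missing on each outcome.

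The reasons to change are to avoid needless selection and to keep secondary data. Their size depends on missingness rates that the SAP does not give.

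**What to change.** 1. In section 6.2.1.3, and in section 6.4 for defined daily doses, analyse each outcome in all consented participants, as randomised, with that outcome observed. In the time-to-event models, keep censored participants up to their last known follow-up.
2. In sections 4.3, 6.2.1.2 and 6.2.5, analyse each co-primary on its own observed cases and make the joint set the sensitivity analysis.
3. State the number excluded for missing data, by arm, for each analysis, next to the intention-to-treat label.

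The co-primary part needs no new modelling, because both analyses are already planned. The secondary part means refitting the Table 7 models on larger sets.

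There is a real downside. The deviation log lists post-hoc work dated 24/06/24 to 09/12/24, so analyses have been run and results are known. Changing the primary population of an open-label non-inferiority trial at this stage could look results-driven. The change should therefore be recorded in the deviation log with its reason, and results from both populations reported side by side for the co-primary and the secondary outcomes.
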